Identifiers:	NCT01806168
Unique Protocol ID:	H12-01578
Secondary IDs:	V12-01578
Brief Title:	rTMS in the Treatment of PTSD

Protocol V3.0 December 10, 2012

Posttraumatic stress disorder (PTSD) is a debilitating psychiatric condition in response to one or more traumatic events including interpersonal violence, accidents, disasters or military action. PTSD can occur at any age and is characterized by clusters of symptoms of consisting of (a) event re-experience, (b) avoidance, and (c) hyper-vigilance (1). In the US, the lifetime prevalence of PTSD in the general population is estimated at 7.5% while in Canada it is estimated at 9.2% (2;3). PTSD in civilian (ie: non-combat veterans) populations has been associated with higher health care costs in comparison to those with Major Depression, and associated with higher costs even when adjusted to depression and other comorbidities (4;5).

Pharmacological and psychological modalities for PTSD are intended to ameliorate symptoms and improve function. A wide range of treatments have been examined and used clinically to treat PTSD. These include antidepressants such as selective serotonin reuptake inhibitors (SSRIs) (6-11), and therapies such as Eye Movement Desensitization and Reprocessing, and Trauma Focused Cognitive Behavioral Therapy (12-16). A systematic review conducted by the National Institute for Clinical Excellence found there was some evidence for psychological treatments in comparison to wait-listed controls, and limited evidence for the use of pharmacological treatments compared to placebo in patients with PTSD (17).

Repetitive transcranial magnetic stimulation (rTMS) is a well-tolerated and non-invasive treatment that utilizes a high powered magnetic field to create electromagnetic energy to depolarize cortical neurons up to 3 cm below the surface of the scalp. The treatment is delivered by a magnetic coil placed at the surface of the scalp below the target brain area while the patient is fully awake, and no anesthesia is required. Depending on the frequency of the stimulation, it can enduringly increase or decrease brain activity in specific brain regions resulting in changes in monoamine levels (18;19) and brain metabolism (20). Very few adverse events are experienced by patients. The occurrence of a seizure during rTMS is extremely rare and only 16 cases have been reported in the literature through decades of research and clinical practice worldwide with tens of thousands of patients. The frequency of seizure with rTMS is not entirely clear. Nevertheless, it is a rare risk that is always discussed during the consent process, and those at elevated risk for seizures (eg: prior history of seizures, on medications or substances known to trigger seizures) are screened out. No seizures have ever occurred at our VGH rTMS clinic.

Repetitive transcranial magnetic stimulation has been shown to be safe and effective in the treatment of major depressive disorder (MDD) (21-41) is now an approved treatment for MDD by Health Canada (since 2002) and the U.S. Food and Drug Administration. The parameters of rTMS treatment include location (usually targeting the dorsolateral prefrontal cortex [DLPFC]), hemisphere (right or left), and intensity. Studies have shown high frequency (>3Hz) rTMS can lead to long-term potentiation, and low frequency (1 Hz) rTMS can can lead to long-term inhibition of neurons, both of which can be effective in treating MDD through direct and indirect changes (42;43). For depression, both high frequency (10-20 Hz) rTMS over the *left* DLPFC and low frequency (1 Hz) rTMS over the *right* DLPFC have shown efficacy (44).

There is now emerging evidence of efficacy of rTMS in the treatment of other psychiatric disorders such as panic disorder and anxiety (45-53). However, the utility of rTMS in the treatment of PTSD has not been extensively studied and only a limited number of studies exist with small sample sizes, and differing methodologies. PTSD can lead to abnormal changes in brain metabolism in certain cortical and subcortical areas. Two of the most frequent positron emission tomography (PET) and functional rTMS & PTSD Protocol V3.0 2 December 10, 2012

magnetic resonance imaging (fMRI) findings suggest decreased activity in the medial prefrontal cortex (mPFC) and the anterior cingulate cortex, while increased amygdala activation is commonly seen (54;55). These brain regions have reciprocal connections to DLPFC so by altering brain function in one accessible (to rTMS) region such as the DLPFC, it can indirectly lead to changes in other regions (56). Moreover, studies of those with PTSD have shown greater abnormality in the right hemisphere compared to left hemisphere, making the right side a more specific target for brain stimulation (57). These changes could theoretically lead to improvement in PTSD symptoms.

Preliminary uncontrolled studies suggest that rTMS has an effect on PTSD symptoms. Grisaru and colleagues treated 10 patients with *bilateral* rTMS using 0.3 Hz for 30 stimuli in a single session (58) while McCann et al. treated two patients for 10 sessions of 20 Hz rTMS over the *left* DLPFC (59). Both studies showed improvement in core PTSD symptoms, but the effects were transient. Rosenberg examined the effects of rTMS with *left* DLPFC at 1 Hz or 5 Hz in 12 patients with comorbid PTSD and MDD (60), and found large effects on depressive symptoms and smaller, but statistically significant, improvement in PTSD symptoms.

The results of randomized controlled trials (RCTs) of rTMS for PTSD have also been promising. In a double-blind, sham-controlled RCT, Cohen et al. examined the efficacy of 14 days of rTMS over the right DLPFC, comparing low frequency (1 Hz) to high frequency (10 Hz) in 24 patients with PTSD (61). Results indicated significant improvement in core PTSD symptoms for patients in the 10 Hz treatment group compared to sham, but not the 1 Hz group. Boggio et al. conducted a double-blind, sham-controlled RCT in 30 patients diagnosed with PTSD (62). Patients were randomized to either sham or high frequency (20 Hz) rTMS for two weeks, over right or left DLPFC. Results showed that both right and left 20 Hz rTMS significantly reduced PTSD symptoms, but the effect was slightly larger on the left side. The reduction in PTSD symptoms was still present at 3-month post-treatment follow-up. Only one study by Osuch et al. examined the effects of rTMS in combination with psychotherapy (63). In a sham-controlled, cross-over study design, 9 patients were randomized to low frequency (1 Hz) or sham rTMS to the right DLPFC rTMS in conjunction with imaginal exposure therapy. Results showed no effect for 1 Hz rTMS compared to sham, but the small sample size likely led to a Type II error. Finally, Watts et al. conducted the most recent sham-controlled RCT of 20 patients with PTSD randomized to sham or right DLPFC low frequency 1 Hz rTMS over 10 sessions, and found significant improvement in PTSD and depressive symptom scores in the active group over the sham, and this change sustained up to 2 months post-rTMS (64).

The results of these studies suggest that rTMS targeting the right DLPFC can ameliorate symptoms of PTSD, but there are discrepant results about the efficacy of low frequency (1 Hz) vs. high frequency (10-20 Hz). Subjects tolerated the procedure well with no cognitive dysfunction and low dropout rates. Furthermore, the utility of rTMS in conjunction with other therapies such as psychotherapy is unclear, given the one small study to date.

The rTMS program at Vancouver General Hospital (VGH) currently focuses on the treatment of patients with depression. Patients typically receive 20-30 treatment sessions over a 4-6 week period. Sessions are conducted on consecutive days, five days a week, by a rTMS-clinic registered nurse under the supervision of a psychiatrist trained in rTMS. Each session lasts approximately 30 to 40 minutes. The clinic is currently situated right within Centennial Pavilion with ready access to emergency response teams and equipment in the unlikely event of a serious adverse reaction occurring during the treatment. The clinic is slated to move to Willow Pavilion in July 2012, which also has ready access to emergency response.

The Outpatient Psychiatry Program (OPP) PTSD program at the VGH Health Centre consists of a twophase, 18 week psycho-educational and behavioural skills program developed from the work of Ogden, Harris, and Najavits aimed at reducing symptoms of PTSD (65-67). Phase One is eight weeks long and includes psychoeducation about psychological trauma. Phase Two is 10 weeks long, and is designed to address longer term or complex traumatic stress disorders. The second phase is based on two models: Trauma, Recovery, and Empowerment (TREM) and Seeking Safety (66;67). Patients are referred from community care providers and are expected to complete the 18 week program if accepted. These patients are not combat veterans since there is already another existing resource for treating those patients elsewhere. Preliminary data from our clinic indicate that those patients completing Phase 1 of our program have very little improvement in their PTSD symptom scores, but Phase 2 can have a greater impact.

The presence of both programs at one site provides a unique opportunity to examine both the short and longer-term effects of rTMS as stand-alone treatment and in combination with psychotherapy. There is a break of 3-4 weeks between Phase 1 ending and Phase 2 beginning, so this period of time allows for rTMS to be conducted for patients willing to undergo this treatment.

In Canada, there are no restrictions for the range of mental disorders that rTMS can be used for in treating patients, although MDD is the condition that is the most commonly treated. Based on reports in the literature, we anticipate that right sided rTMS is as safe and tolerable as left-sided rTMS. Therefore, we propose to conduct a study of rTMS in patients with PTSD who are starting the group psychotherapy program at VGH. Since previous research has shown a discrepancy between the efficacy of high versus low frequency rTMS on the symptoms of PTSD, we will examine the use of high (10 Hz) versus low (1 Hz) frequency rTMS delivered over the right DLFPC of patients suffering with PTSD symptoms unrelated to combat. Standardized evaluations will be done to assess for clinical improvements in the PTSD, depressive and anxiety symptom clusters, and for tolerability with monitoring of adverse events and dropout rates.

Primary Hypothesis

The primary hypothesis is that high frequency (10 Hz) rTMS over the right DLPFC will be superior to low frequency (1 Hz) in reducing scores as measured by the PTSD Check List.

Research Method

Subject Recruitment

Subjects will be recruited from the PTSD treatment program conducted at the VGH Outpatient Psychiatry Program (OPP). Mid-way during the Phase 1 of the group psychoeducational program, patients will be approached regarding their willingness to participate in the study. Those subjects expressing interest will receive a description of the study along with an informed consent form that the client can sign if s/he chooses to participate. Should the patient agree to participate, a screening interview will be administered to determine if s/he meets the inclusion / exclusion criteria.

Inclusion criteria: (1) primary diagnosis of PTSD as determined by a structured interview (Mini International Neuropsychiatric Interview, MINI (68)); (2) no change in psychotropic medications within 4 weeks before the start of rTMS; (3) age greater than 19 years and less than 70 years; and (4) competent to give informed consent.

Exclusion criteria: (1) any non-fixed metal object or implant (including cochlear implants) in brain, skull, scalp, or neck within 30 cm of the magnetic rTMS coil; (2) implantable devices, including cardiac pacemakers and defibrillators; (3) other contraindications to rTMS, including history of seizures (except childhood febrile seizures) or recurrent and unexplained syncope, first degree relative with a history of epilepsy, treatment with a medication known to substantially decrease the seizure threshold, and pregnancy; (4) psychiatric diagnoses of psychosis or psychotic disorder (including psychotic depression), bipolar type 1 disorder, organic mental disorders; (5) substance abuse/dependence within the past 3 months; (6) active suicidal risk as judged by the clinician; (7) borderline or antisocial personality disorder; (8) acute medical illness, including cancer; (9) any significant central nervous system disorder such as brain mass, stroke.

Research Design

This will be a prospective, 2-week, double-blind (subject and evaluator) randomized controlled pilot study to assess the effect of repetitive transcranial magnetic stimulation (rTMS) in patients with a confirmed diagnosis of PTSD. The rTMS will target the right DLPFC. Subjects will be randomized into either 1 Hz or 10 Hz treatment arms, or sham arm.. The rTMS will be administered between Phase 1 and 2 of the PTSD OPP, so there will not be concurrent group therapy during the 2-week rTMS sessions. Outcome measures will be assessed at baseline, after 1 week and 2 weeks (completion) of rTMS, and at follow up after Phase 2 of the PTSD OPP group psychotherapy program (approximately 10 weeks after completion of rTMS).

Primary Outcomes

 Changes in PTSD symptoms as measured by – Clinician Administered PTSD Scale (CAPS (69)), patient rated Post Traumatic Stress Disorder Checklist Civilian (PCL-C).

Secondary Outcomes

- Changes in symptoms as assessed by:
 - For Depression clinician administered Hamilton Depression Rating Scale (17 items) (HAMD), patient rated Quick Inventory of Depressive Symptomatology-Self-report (QIDS-SR (70)).
 - For Anxiety Beck Anxiety Inventory (BAI), Generalized Anxiety Disorder Assessment (GAD-7).
 - These are all standardized, validated symptom measures that are widely used in clinical and research settings. The QIDS-SR, GAD-7 and PCL-C are also used as routine clinical outcome measures in the PTSD OPP.
- Adverse events, safety, and tolerability
 - Incidence of serious and non-serious adverse events attributable to rTMS (eg: headache, scalp pain, facial pain, dizziness, tinnitus, light-headedness, syncope, seizure).
 - Montreal Cognitive Assessment (MOCA).

Procedures and Methods

After giving written, informed consent, subjects will undergo baseline assessment measures. Eligible subjects will be randomized to one of three treatment arms (high or low frequency rTMS, or sham rTMS). Concealment of allocation will be accomplished using a computerized randomization program that reveals treatment allocation only after the unique subject identifier is entered. The randomization codes will be available on a 24-hour basis in the (unlikely) event that the blind needs to be broken for clinical reasons. The subject will be blind to treatment condition because they will be unaware of the rTMS frequencies or sham condition used in the study. The rTMS nurse will be unblinded, but the

evaluator for clinician-rated assessments will be blind to treatment conditions. The rTMS nurse will not interact with the evaluator, and should any unblinding occur, the evaluator will be replaced.

The secondary outcome measures will be repeated weekly after rTMS session number 5 and 10 (or at termination, for early withdrawals). Adverse events and severity (mild, moderate, severe) will be recorded at each session. Serious adverse events will be defined according to standard Health Canada definitions as those which: a) result in death; b) are life threatening; c) are severely or permanently disabling; d) require inpatient hospitalization; e) result in an incidence of cancer; f) result in a drug overdose or reaction after drug withdrawal. All subjects who withdraw from the study will be asked to state a reason for withdrawal. The outcome measures will also be repeated after completion of the Phase 2 group psychotherapy program (about 10 weeks following completion of the rTMS).

The blind evaluator(s) will receive standardized training to establish inter-rater reliability using videotaped interviews. Reliability of outcome assessment will also be enhanced by using structured interview guides for the HAMD and CAPS.

Interventions (rTMS Stimulation)

The motor threshold is determined during the first session by applying TMS over the motor cortex in order to get the minimal level of stimulus intensity from the device which will create a contraction in the contralateral abductor pollicis brevis muscle of the thumb. The DLPFC will be targeted by measuring 6 cm anterior to this motor cortex landmark, along the sagittal plane, as the patient will be wearing a swimmer's cap. The intensity of the stimulus is set by going 100-120% of the intensity which determined motor threshold. rTMS therapy over the right DLPFC will be given on 5 consecutive days every week for two weeks for a total of 10 therapy sessions using a Magstim Super Rapid2 (Magstim Company Ltd., Carmarthenshire, Wales, UK) with a Rapid-2 Air Film Coil.

Subjects will receive either active rTMS to the right side at 1 Hz or at 10 Hz, or sham treatment for 37.5 minutes per session. The stimulus parameters that will be chosen for treating subjects will be similar to the parameters currently used at our clinic to stimulate patients with depression. A clinic nurse will always be present to deliver the treatment, and a supervising rTMS psychiatrist will oversee the appropriate placement and intensity of the coil, as well as responding to any adverse event which may arise. Each subject is given appropriate ear protection due to the intensity of the sound from each treatment pulse delivered by the device. Subjects who experience some initial discomfort during the session, such scalp or facial irritation, will prompt trying a different orientation of the coil at the same DLPFC site, which will usually relieve the discomfort. Subjects may leave immediately on their own after the treatment is completed, and may even drive, unless a serious adverse event occurred.

SAMPLE SIZE

Based on the standardized effect size for the primary outcome, the PTSD Check List, as determined by the previous RCT (71;72) (d=1.4), and with alpha set to 0.05 and 80% power, we estimated a sample size of nine subjects/condition. Note that this effect size is regarded as a large effect and is clinically significant.

Data Analysis

All randomized subjects will be included in the analysis based on intent-to-treat. Missing data will be imputed using last observation carried forward (LOCF). The pre-specified primary efficacy endpoint is the adjusted mean change from baseline to endpoint (2 weeks) on the PTSD Check List using LOCF. All comparisons will be analyzed using ANCOVA adjusting for baseline value. The secondary outcomes will also be analyzed using a similar analysis, when appropriate. Post hoc analyses will also rTMS & PTSD Protocol V3.0 6

examine observed case data. Categorical data (such as proportions of the sample with adverse events) will be analyzed using chi-square tests or Fisher's test where cell sizes warrant.

Reference List

- (1) APA. American Psychologic Association. Diagnostic and statistical manual of mental disorders . 4 ed. Washington, DC: APA; 1994.

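### Does restricting the safety outcome to events attributable to rTMS, with no attribution procedure, bias the comparison with sham?

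*Combined protocol and SAP*

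**What the plan says.** Under Secondary Outcomes (Adverse events, safety, and tolerability) the incidence outcome is "Incidence of serious and non-serious adverse events attributable to rTMS". An open list of examples follows, all recognisable side effects of stimulation, such as headache, dizziness and seizure.

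Procedures and Methods sets the recording rule: "Adverse events and severity (mild, moderate, severe) will be recorded at each session". Serious events are defined there by seriousness criteria alone, with no causality element. The Data Analysis section has one sentence on adverse events: "Categorical data (such as proportions of the sample with adverse events) will be analyzed using chi-square tests", with Fisher's test as the alternative for small cells. Neither the recording rule nor the analysis sentence mentions attribution.

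On the arms and the blind, Procedures and Methods says "Eligible subjects will be randomized to one of three treatment arms (high or low frequency rTMS, or sham rTMS". It also says "The rTMS nurse will be unblinded", whereas the "evaluator for clinician-rated assessments will be blind to treatment conditions". No section assigns a causality judgement to the nurse, the evaluator or the supervising psychiatrist.

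**The concern.** The outcome definition contains a filter that the recording and analysis text lacks, so two analysts could count different numerators for the same outcome. The definition can be read in two ways.

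1. The phrase names types of event that are typical of stimulation and are counted alike in all three arms. This causes no bias.
2. Each event is judged case by case as caused by rTMS or not. The plan would then lack criteria, an assessor and blinding for that judgement. The person delivering sessions knows the arm, and the blinded evaluator is assigned only to the clinician-rated scales.

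Under the second reading, a headache after sham could be dismissed because no active stimulation was given, while the same headache after 10 Hz would count. The active-versus-sham tolerability comparison would then partly measure the filter. With about nine subjects per arm, moving a few events can change a test result.

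**Working it through.** **Which reading the text supports**

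| Place in the protocol | Attribution limit? |
|---|---|
| End of the background text: tolerability assessed by monitoring adverse events and dropout | No |
| Secondary Outcomes: incidence outcome | Yes |
| Procedures and Methods: recording at each session, with severity | No |
| Procedures and Methods: definition of serious events | No |
| Interventions: psychiatrist responds to any adverse event | No |
| Data Analysis: proportions with adverse events compared | No |

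One statement of six carries the qualifier, and it is followed by a list of event types. The plan records occurrence and severity but no relatedness rating, so no planned data item exists from which a case-by-case filter could be applied. Procedures and Methods also calls the control sham rTMS, so sham events are not excluded by the wording. The first reading fits every statement. The second needs a step that no section describes.

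**What the filter could do if it were applied anyway**

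Inputs:
- Nine subjects per arm, from the Sample Size section. That figure reproduces: d = 1.4, two-sided alpha 0.05 and 80% power give 9 per arm by the normal approximation (9.08 with the t distribution; power at 9 is 79.6%).
- Assumed, because the documents give no rates: the same true rate *r* of subjects with an event in every arm; 90% of active events attributed; a share *s* of sham events attributed, with *s* = 90%, 70%, 50% or 10%.

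Counted rate, active arm = 0.90 × *r*. Counted rate, sham = *s* × *r*. False difference = *r* × (0.90 − *s*). For example, *r* = 10% and *s* = 10% gives 0.10 × 0.80 = 8 points. One subject in nine is 11.1 points, so this is 8 / 11.1 = 0.72 of a subject.

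False difference in percentage points:

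| True rate *r* | *s* = 90% | 70% | 50% | 10% |
|---|---|---|---|---|
| 10% | 0 | 2 | 4 | 8 |
| 20% | 0 | 4 | 8 | 16 |
| 30% | 0 | 6 | 12 | 24 |
| 50% | 0 | 10 | 20 | 40 |

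Chance of two-sided Fisher p ≤ 0.05, one active arm against sham, by exact enumeration of the two binomial counts (9 versus 9). The last column counts all events, with no filter:

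| True rate *r* | *s* = 90% | 70% | 50% | 10% | All events |
|---|---|---|---|---|---|
| 10% | 0.05% | 0.04% | 0.04% | 0.05% | 0.07% |
| 20% | 0.5% | 0.5% | 0.6% | 1.1% | 0.7% |
| 30% | 1.4% | 1.5% | 2.1% | 5.4% | 1.6% |
| 50% | 2.1% | 3.2% | 7.1% | 28.9% | 2.1% |

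The exact three-arm test (9/9/9, both active arms at 0.90 × *r*) is more sensitive but has the same pattern. At *s* = 10% its rejection chance is 0.5%, 3.5%, 11.4% and 42.7% for *r* = 10%, 20%, 30% and 50%. With all events counted it is 0.5%, 1.9%, 3.0% and 3.0%.

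The nominal 5% is passed only at *r* = 30% with *s* = 10%, and at *r* = 50% with *s* = 50% or 10%. This holds for both tests. The background text points toward low rates: "Very few adverse events are experienced by patients", and of earlier trials, "Subjects tolerated the procedure well with no cognitive dysfunction and low dropout rates".

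**The case for a change.** The strongest case for a change is that the mismatch is real and cheap to repair. The list of examples is open, so an unlisted event still needs a decision on whether it counts, and the plan gives no rule. The terms for the control also vary: sham rTMS in Procedures and Methods, but sham treatment, set against active rTMS, under Interventions. With nine per arm the numerator can matter. Taking invented counts of 6/9 active and 3/9 sham with any event, Fisher's p is 0.35. If attribution removed sham events so that 2, 1 or 0 remained, p would be 0.15, 0.0498 or 0.009.

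The textual points stand: the qualifier appears once, it has no procedure behind it, and it is loosely worded. The inference to bias is weaker. It needs an assessor, a judgement and knowledge of the arm at the moment of judging, and the plan sets up none of the three as a step in counting events. That the unblinded nurse would do the judging is an inference. The background text's statement that adverse events are very few lends little support to counts such as 6/9, although the documents give no per-subject rate that would exclude them.

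A rewrite would also gain little. Counting all events by arm regardless of attribution is what the Data Analysis sentence already describes. Confining the count to the span from first to last session, one way to tie it to the recording rule, would do harm: subjects are assessed again about 10 weeks after rTMS, and serious events that come to light in that interval would be left out.

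**Conclusion.** The concern does not call for a change. This is a gap in wording that an analyst fills sensibly by following the Data Analysis section: count subjects with adverse events in each randomised arm, sham included. The events and their severity are to be recorded at each session, so the unfiltered comparison is available from planned data.

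The effect is nil if the phrase names event types. It is negligible in the two-arm test if a filter were applied at event rates of 10% to 20% (at most 1.1%). It is large only when a high event rate meets a strong loss of sham events (28.9% two-arm and 42.7% three-arm at a 50% rate with 90% versus 10% attribution). These figures rest on assumed event and attribution rates, because the documents supply none.

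Tolerability is a secondary outcome in a pilot, with no safety hypothesis or decision rule attached. The primary comparison on the PTSD Check List is unaffected. Bias from unblinded elicitation or severity grading is a separate matter that removing the qualifier would not touch.

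### Does the plan need a stated window linking baseline, eligibility check and randomization to the first rTMS session?

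*Combined protocol and SAP*

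**What the plan says.** All references are to the combined protocol and SAP.

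- **Background, description of the outpatient PTSD program.** "Phase One is eight weeks long and includes psychoeducation about psychological trauma". "There is a break of 3-4 weeks between Phase 1 ending and Phase 2 beginning", and rTMS is to be given in that break. The clinic's preliminary data are that "those patients completing Phase 1 of our program have very little improvement in their PTSD symptom scores".
- **Subject Recruitment.** "Mid-way during the Phase 1 of the group psychoeducational program, patients will be approached regarding their willingness to participate in the study". Interested patients receive the study description and consent form. "Should the patient agree to participate, a screening interview will be administered to determine if s/he meets the inclusion / exclusion criteria".
- **Inclusion criterion 2.** "no change in psychotropic medications within 4 weeks before the start of rTMS".
- **Procedures and Methods.** "After giving written, informed consent, subjects will undergo baseline assessment measures". "Eligible subjects will be randomized to one of three treatment arms".
- **Research Design.** The study is described as lasting two weeks, with rTMS placed between the two phases. Outcomes are measured at baseline, after each of the two treatment weeks, and again after Phase 2, about 10 weeks after rTMS ends.
- **Data Analysis.** The primary endpoint is the two-week change from baseline on the PTSD Check List, by ANCOVA on baseline. All randomized subjects are analysed, with last observation carried forward (LOCF). Observed-case analyses are planned post hoc.

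Only the approach to patients has a date. Consent, screening, baseline and randomization have an order but no stated interval to session 1, and no recheck before session 1 is described.

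**The concern.** A reader who follows the steps in the order written, starting from the only dated one, can put consent, screening, baseline and randomization in the middle of Phase 1. Three things would then go wrong.

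1. The nominal two-week change would include about four weeks of group sessions. Within-arm change could not be credited to rTMS alone, and an older baseline would probably be a weaker ANCOVA covariate.
2. The medication criterion looks back four weeks from the start of rTMS. It could not be verified at a screening interview held before that period had begun, or just as it opened.
3. A subject who left or became ineligible before session 1 would already be randomized. That subject would stay in the analysis set, probably with the baseline value carried forward as no change. With nine subjects per arm, each such case matters.

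**Working it through.** **The plan's own figure.** The Sample Size section gives d = 1.4, alpha 0.05, 80% power and nine per condition. The two-sided normal approximation gives n = 2 × ((1.960 + 0.842)/1.4)² = 8.01, rounded up to 9. The t-test calculation gives 79.6% power at n = 9. The figure reproduces, and the timing of baseline does not enter it.

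**Earliest timeline the text allows.**
- Phase 1 remaining at its midpoint: 8/2 = 4 weeks.
- Latest start of a two-week course within the break: 3 − 2 = 1 week into a 3-week break, or 4 − 2 = 2 weeks into a 4-week break.
- Approach to session 1: 4 + 0 to 4 + 2 = 4 to 6 weeks.
- Approach to the two-week endpoint: 6 to 8 weeks.
- Opening of the four-week medication window: 4 − 4 = 0 to 6 − 4 = 2 weeks after the approach.

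These ranges apply only if baseline and the other steps follow the approach at once, which the protocol does not say.

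**What the other passages imply.**
- A two-week study with a two-week change from baseline fits only if baseline is near session 1. A mid-Phase 1 baseline would make the interval three to four times its label (6/2 = 3, 8/2 = 4).
- Only eligible subjects are randomized, and one inclusion criterion covers the four weeks up to the start of rTMS. Read together, these mean that eligibility cannot be fully known, and so allocation cannot properly be released, until close to session 1. The early sequence conflicts with the protocol's own criterion.

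**Is there room near session 1?** The course uses 10 weekdays. A 3-week break has 15 and a 4-week break has 20, leaving 15 − 10 = 5 to 20 − 10 = 10 weekdays. These must also hold the assessment after session 10. It is tight but workable.

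**Effect on the primary contrast.** The rest of Phase 1 is common to all arms and is expected to change scores little. Loss before session 1 cannot be a response to treatment, and subjects are blind to their arm. Neither favours 10 Hz or 1 Hz in expectation. What remains is dilution, at 1/9 = 11% of an arm per never-treated subject, and some loss of precision.

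**Can the precision loss be sized?** The ANCOVA confidence interval width is proportional to √(1 − r²), where r is the baseline-to-endpoint correlation. The documents give no r. If staleness lowered an assumed r of 0.7 to 0.65, 0.6 or 0.5, the width would grow by √(0.5775/0.51) − 1 = 6%, √(0.64/0.51) − 1 = 12% or √(0.75/0.51) − 1 = 21%. The answer is set by the assumption. Power figures have the same weakness: they also need an assumed dropout rate and a decision on whether d = 1.4 is in raw-score or change-score units, which the protocol does not state. None is relied on here.

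**The case for a change.** The strongest case for a change rests on eligibility and needs no assumed correlation. The only eligibility check described follows the patient's agreement, and agreement is sought before the medication window has run. Other criteria can also change over 4 to 6 weeks, such as pregnancy, recent substance abuse, suicidal risk and acute illness. The analysis rule keeps everyone randomized and makes no separate provision for those never treated. A sentence fixing the order would cost little, since the randomization program already withholds the allocation until the subject identifier is entered.

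The factual part stands: no window and no recheck are written down. The available mitigation is partial. The observed-case analyses are post hoc. Assessment at early withdrawal is stated for the secondary measures. The PCL-C is collected routinely in the program, but the protocol does not say that those scores serve as the study baseline.

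The inference to a faulty plan does not stand. A criterion counted from the start of rTMS itself obliges whoever applies it to look at the period up to session 1. Nothing in the text instructs the site to measure baseline or release the allocation in mid-Phase 1.

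**Conclusion.** No change to the plan is needed. The omission is real, but it is missing operational detail and not a rule that gives a wrong result. The two-week design and endpoint, the medication criterion tied to the start of rTMS, and the restriction of randomization to eligible subjects all lead a competent site to complete these steps after Phase 1 and shortly before session 1. The 5 to 10 spare weekdays in the break make that feasible.

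The 4-to-6-week gap is a worst case that requires every step to follow the approach promptly. Even then the between-arm contrast is unbiased in expectation, given randomization and the clinic's own finding of very little Phase 1 improvement. The remaining cost is 11% of an arm for each never-treated subject, plus a precision loss that the documents do not allow one to size. The judgement assumes that the site reads the two-week wording and the medication criterion in their ordinary sense. If the conduct records showed baseline or allocation in mid-Phase 1, within-arm changes would need to be read with that in mind.
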